11.5. Description of the Health Economics Methods

A prospective economic evaluation at 12 months, conducted from an NHS and personal social services perspective, will be integrated into the trial design. All economic analyses will be performed both on a perprotocol and on an intention-to-treat basis, as per statistical analyses of outcomes. Given that this economic evaluation will be conducted alongside a non-inferiority trial, per protocol estimates may retrieve more conservative estimates. The economic evaluation will estimate the difference in the cost of resource inputs used by participants in the two arms of the trial, allowing comparisons to be made between the surgical and non-surgical treatment of unstable ankle fractures in adults aged 60 years or less and enabling costs and consequences to be compared.

Consequences of interest will be quality-adjusted life years (QALYs) at 12 months and clinical primary outcome of the OMAS score²¹ at four months, but all other secondary outcomes will also be reported in a cost-consequences table and follow NICE guidelines.³⁶ Given the importance of returning to work and usual activities to the younger patients with ankle fracture, we will separately report productivity losses from paid and unpaid work and need of informal care.

Resources used to deliver the treatment in both arms will be valued using a macro-costing approach when possible, using department of health and social care reference costs for secondary care resources³⁷, unit costs for health and social care for community resources³⁸, average weekly earnings for productivity losses ³⁹ and patient self-reported expenses. Costs will be reported grouped by secondary care resource use, community-based resource use (including primary and social care) and productivity losses (including lost time off-work, leisure and informal care). The aggregate health and social care at 12 months will also be

reported. Costs and QALYs will be estimated using regression analyses controlling for baseline scores and trial stratification variables.

In the economic analyses, given the number and nature of resource use data collection methods and timepoints, we expect the amount of missing data to be considerable. Multiple imputation methods will be used to impute data both in the per protocol and ITT analyses. We will jointly input cost categories and health outcomes if computationally feasible and supply imputed primary outcome data estimates for the statistical analysis.

The results of the economic evaluation will be reported in cost consequences tables and in cost-effectiveness planes. We will derive incremental net monetary benefit statistics using the NICE recommended thresholds of £20,000 and £30,000 per QALY but also a lower threshold of £10,000/QALY. We will use non-parametric bootstrap estimation to derive 95% CIs for mean cost differences between the trial groups and to calculate 95% bootstrapped CIs for incremental net monetary benefit statistics.

A series of sensitivity analyses will be undertaken to explore the implications of uncertainty around the costing and methodological assumptions on the incremental net monetary benefit statistics and to consider the broader issue of the generalisability of the study results. One such sensitivity analysis will involve adopting a societal perspective for the economic evaluation, which will incorporate direct costs to trial participants, informal care provided by family and friends and productivity losses.

11.6. Long term data analyses

These analyses will not be reported in the initial publications of the trial results (limited to one year follow-up) but will be reported in a separate publication at the end of the five year follow-up period

The long-term follow-up data will be collected to achieve three objectives: firstly, longer-term clinical effectiveness of the two treatments under investigation will be assessed; secondly, we will validate patient-reported hospital healthcare use collected during the trial against data collected from HES, and finally, we will assess the 5-year cost-effectiveness of CCC compared with surgery.

For the validation of hospital healthcare use, we will restrict the analysis to those trial participants who give consent to our accessing their hospital records. A detailed characterisation of the consenting and nonconsenting groups will be undertaken in terms of basic demographics and primary/secondary trial outcome measures to provide context for the longer-term analysis restricted to consenting participants. HES inpatient, outpatient and A&E attendances during the 12-month trial duration will be compared to what was reported by patients through CRFs. Relevant HES records will be identified using OPCS-4 codes corresponding to the CRF wording used for collection of hospital resource use. As the validation will compare the number of attendances to the various hospital services, missing data will not be a problem as a record of hospital attendance in HES will be the only marker required to identify the use of resources.

For the cost-effectiveness analysis, an economic model will be built and populated with observed hospital costs derived from HES (including late complications), outcome data (OMAS and EQ-5D, separately for the cost-effectiveness and cost-utility analyses, respectively) collected annually from trial participants, and plausible assumptions on the extrapolation of trial findings for all other model inputs. As the analysis will be conducted based on costs and outcomes for trial participants, the model will be used to produce results for alternative scenarios or sensitivity analyses on the assumptions and extrapolation of specific parameters collected only during trial duration.

The 5-year long-term patient-reported outcomes (OMAS and EQ-5D) will be analysed using a multilevel mixed-effects model using repeated measures over time nested within participants as described for the

primary (short-term) outcomes. The model will include centre as a random effect and age, gender and fracture instability and other important prognostic factors as fixed effects as planned for the short-term outcomes. This will enable us to include all available data from all time-points. Trends over time will also be examined and if appropriate time by treatment interactions will be added to the model. In addition, an AUC summary statistics will be compared between the two interventions.

Missing data can be expected for both outcome measures at any time point they are collected as well as for resource use questions during the trial. As indicated above, hospital resource use observed in HES will not carry a risk of missing data, but OMAS and EQ-5D will. We will use multiple imputation by chained equations (MICE) for any unanswered question in these. Missing data will be imputed simultaneously for both outcome measures at each point they are collected using linear regression models. Independent variables in the imputation models are likely to include baseline and subsequent values of both outcome measures, use of resources, gender, age at randomisation, and trial arm. Imputations will be run separately by treatment arm and a total of 20 sets of imputed values generated and estimations produced accounting for uncertainty due to imputation.

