9.10. Review of medical notes

At 12 months, the local research team at each centre will review hospital records for the trial participants and collect information on any visits and/or admissions related to the index fracture. These may include details of rehabilitation sessions offered at the treating centre and other outpatient care, including type of clinic visited and frequency, treating health care staff, and whether first appointment or routine follow-up; accident and emergency visits; and day-case and inpatient readmissions to hospital, reason for readmission, procedures and tests performed, and days admitted to various wards.

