10.3. Reporting Procedures for Adverse Events not defined as serious

Adverse events that are unrelated to the intervention or treatment will not be reported.

Adverse events (AEs) that are foreseeable in the treatment of these fractures, and are not defined as SAEs, do not need to be reported immediately, provided they are recorded in the 'Complications' section of the Case Report Forms and/or Patient Questionnaires.

Other adverse events, foreseeable or unforeseeable, that are not in this list, will not be reported.

Foreseeable, related AEs include the following:

- (a) Related to CCC only:
- o loose cast or tight cast requiring reapplication
- failed closed reduction
- o pressure ulcer
- o plaster saw laceration
- (b) Related to surgical treatment only:
- o surgical site infection
- failed fixation
- o prominent implant
- wound dehiscence
- vascular injury

- (c) Related to both treatments:
- o revision surgery, defined as unplanned return to theatre
- symptomatic deep venous thrombosis
- o symptomatic pulmonary embolus
- o compartment syndrome
- o nerve palsy
- o complex regional pain syndrome
- pain/irritation/itchiness from cast

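### Section 11.6 counts hospital attendances in HES but selects the records by procedure codes, so the reference count in the validation of patient-reported use is too low

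*Protocol*

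**What the plan says.** Section 11.6 (Long term data analyses) names three long-term objectives. The second is that "we will validate patient-reported hospital healthcare use collected during the trial against data collected from HES". The validation paragraph then makes these statements:

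- What is compared: "HES inpatient, outpatient and A&E attendances during the 12-month trial duration will be compared to what was reported by patients through CRFs".
- How the HES records are chosen: "Relevant HES records will be identified using OPCS-4 codes corresponding to the CRF wording used for collection of hospital resource use".
- The unit, and the expected completeness: "As the validation will compare the number of attendances to the various hospital services, missing data will not be a problem".
- The reason given for that completeness: "a record of hospital attendance in HES will be the only marker required to identify the use of resources".

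No other selection rule appears. Apart from the 12-month window, the paragraph mentions no diagnosis code, specialty, clinic type, attendance type or date matching. Later in the same section, hospital use seen in HES is again described as free of missing-data risk.

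**The concern.** The unit of the comparison is an attendance, but the filter works on procedures. A procedure-code filter cannot return a record that holds no procedure code. An outpatient review, an emergency visit or an admission can be a genuine attendance for the fracture without one.

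The protocol shows elsewhere that such use is of interest. Section 9.10 (Review of medical notes) covers clinic type and frequency and goes on to "accident and emergency visits; and day-case and inpatient readmissions to hospital, reason for readmission, procedures and tests performed, and days admitted to various wards"; procedures are one item among several. Section 10.3 lists foreseeable complications such as "symptomatic deep venous thrombosis", and an attendance for one of these need not carry a matching procedure code.

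HES is the reference standard here, so the error falls on the patients' reports. A visit that the filter drops is treated as one that did not take place, and a correct report of it is scored as over-reporting. Because the section regards HES as complete, it plans no check that would reveal the loss.

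**Working it through.** **No figure to reproduce.** The protocol gives no number for the validation: no expected count, no agreement target, and no share of attendances with an OPCS-4 code. The trial's sample size and margin do not bear on this point. The check is therefore a comparison of statements, followed by an illustration on assumed values.

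**Step 1: statements side by side (all from section 11.6).**

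| Element | What is stated | Level |
|---|---|---|
| Quantity compared | Attendances in three HES datasets over 12 months | Attendance |
| Unit | Number of attendances | Attendance |
| Selection of relevant records | OPCS-4 codes matched to CRF wording | Procedure |
| Marker of use | Existence of an attendance record, and nothing more | Attendance |

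The third row does not fit the other three.

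**Step 2: the OPCS-4 rule governs.** Let N be the true number of relevant attendances and s the share with a matching OPCS-4 code. Suppose that patients report exactly N.

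- HES count = s × N
- Under-count in HES = 1 − s
- Apparent ratio of self-report to HES = N / (s × N) = 1 / s

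| s (assumed) | Under-count (1 − s) | Apparent ratio (1 / s) |
|---|---|---|
| 1.0 | 0% | 1.00 |
| 0.9 | 10% | 1.11 |
| 0.7 | 30% | 1.43 |
| 0.5 | 50% | 2.00 |
| 0.3 | 70% | 3.33 |
| 0.1 | 90% | 10.0 |

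The bias vanishes only at s = 1. For any smaller s its direction is fixed: HES too low, patients apparently over-reporting. The values of s are illustrative and nothing in the protocol favours one of them.

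**Step 3: the attendance-record statement governs.** Every HES attendance in the window counts. The loss in step 2 does not arise, but relevance is no longer defined. If the patient form asks only about the fracture, and U attendances have other causes, HES holds N + U against a correct report of N. The ratio N / (N + U) is below 1 whenever U is above 0, so accurate patients would appear to under-report. The patient form is not shown, so this direction is conditional.

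**Step 4: both together.** The two statements define different sets of records, and the set chosen can change the sign of the apparent reporting error. Neither gives a sound count of fracture-related attendances.

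**The case against.** The strongest reply is that the attendance-record statement shows the real intention: a visit counts because HES holds a record of it, and the OPCS-4 sentence is loose drafting. On that reading no attendance is lost. This has force, and it is why the loss is tied here to following the OPCS-4 sentence as written. It does not rescue the paragraph. The OPCS-4 sentence is the only one that says how relevant records are found, and setting it aside leaves no rule for relevance.

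A second reply is that code lists belong in the SHEAP, and that the CRF wording to which the codes are matched is not shown. A code list can indeed wait. The choice of a procedure classification to find attendances is already fixed in the protocol, though, and a longer list of procedure codes would not pick up records that carry none. It is also fair to say that section 9.10 describes the notes review and not the patient questionnaire. It shows what hospital use interests the trial, not the exact items patients answer.

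Three stronger readings are tempting, and the protocol does not support them.

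- **A definite size.** A reader might infer that half or more of the attendances would be missed. No share is given, so no size can be claimed.
- **Distorted 5-year costs.** A reader might infer that late complications managed without a procedure would be costed at zero. The OPCS-4 sentence sits in the validation paragraph. The cost-effectiveness paragraph is separate, names no such filter, and says that late complications are included. Section 12 describes the linkage in terms of interventions on the ankle, but sets no costing rule.
- **Imbalance between arms.** A reader might infer that casting generates more uncoded clinic care. Section 9.6.2 says only that some participants will need the cast reapplied, section 9.6.4 leaves monitoring in both arms to the surgeon, and some recasting may itself be coded as a procedure.

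**Conclusion.** The point holds as a fault in a stated rule. If section 11.6 is followed as written, the HES reference count omits attendances without a matching procedure code, and accurate patient reports look inflated by a factor of 1/s. The direction is known for any s below 1; the size is not.

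This rests on two assumptions: that OPCS-4 has its ordinary technical meaning as a classification of procedures, which the protocol does not spell out, and that it is the only filter, as the text has it. If the attendance-record statement is meant to govern, the defect becomes the absence of any definition of relevant use. The paragraph needs correction either way.

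The reach is limited to the validation objective, one of three for long-term follow-up and reported separately. The primary OMAS analysis is untouched. Effects on the 5-year costs and on the comparison between arms are possible but not established. It should be corrected, but it does not threaten the trial's main conclusion.

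**What to change.** Reword section 11.6 as follows.

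1. Select relevant records at attendance level, separately for inpatient, outpatient and emergency data, using dates together with attendance type, specialty or diagnosis, matched to the CRF items.
2. Use OPCS-4 only to classify procedures within attendances already counted.
3. Reconcile the OPCS-4 sentence with the statement that an attendance record is the only marker needed.
4. State which record definition the 5-year HES costs use, whether the same or another.
5. Put the date, specialty, attendance-type and diagnosis fields in the linkage request.

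The cost is a few sentences, a code list and some extra fields. Section 7 places HES collection five years after the last participant is recruited, so the change is cheap if made before the request; finding after extraction that the fields were not supplied would be costly. The drawback is that a broader selection takes in some unrelated attendances. A sensitivity analysis restricted to records clearly tied to the ankle would show how much that matters.

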7. STUDY DESIGN

This trial is a pragmatic, multicentre, randomised non-inferiority clinical trial with parallel economic analysis, with direct participant follow-up to one year, and annual surveillance extending out to five years. The trial will employ 1:1 random allocation, stratified by centre and the presence or absence of posterior malleolus fracture. If non-inferiority is demonstrated, superiority will also be investigated.

A total of 890 participants will be recruited in a minimum of 26 hospital orthopaedic departments within the UK. A member of the research team at the site will screen patients for eligibility, and when this is confirmed by a clinician, a GCP-trained member of the team will approach the patient to explain the study and gain informed consent. This consent will include permission to access data, through NHS Digital, from Hospital Episode Statistics (HES) about their hospital attendances during the 5 years following the index treatment. Participants will complete questionnaires at baseline, and follow-up questionnaires at 8 weeks, 4 months and 12 months after treatment, thereafter they will be contacted annually for a further 4 years. Five years after the date of final participant recruitment, we will collect routine hospital data through a linkage with HES (inpatient, outpatient & emergency department databases). A summary of the participant pathway can be seen in Figure 1.

Data will be collected via an instance of REDCap (Vanderbilt University Medical Center, Nashville, USA), (hosted by OCTRU, The University of Oxford, UK). ²⁶ Baseline data, complications and review of records at the end of the trial will be directly entered onto the database by the local research team. Participants will be contacted for follow-up using email and/or SMS message prompts and invited to complete questionnaires through an online link. A schedule of email and SMS reminders and follow-up phone calls for those participants failing to complete the questionnaires will be outlined in the trial data management plan and approved by the CI and trial statistician.

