9.3. Informed Consent

A member of the responsible clinical team will briefly highlight the study to the patient and introduce a member of the local research team. They will approach the patient and explain the trial. In order to standardise the information provided to the patients, online and written recruitment materials will be made available to local research teams. The local research team will also be able to answer any additional questions that the patient might have.

This will then lead on to an informed consent discussion and if happy to proceed the patient will provide written electronic consent. Patients will be given as much time as possible to consider the information and discuss it with relatives/carers. Qualitative research in these emergency settings has shown that patients do not feel negatively affected by the relatively short time to make this consent decision. It will be clearly stated that the participant is free to withdraw from the study at any time for any reason without prejudice to future care, without affecting their legal rights, and with no obligation to give the reason for withdrawal.

Prospective consent will also be sought to access the participant's personal data within the various data warehouses in the UK that hold information on patients admitted to NHS hospitals. We will use these administrative databases to source additional data for the purposes described in this protocol. For participants treated in England we plan to use admitted patient care, emergency care, outpatient care and critical care datasets within the Hospital Episode Statistics (HES) database; in Scotland, The Scottish Morbidity Register – General/Acute Inpatient and Day Case (SMR01); in Northern Ireland the Acute Episode-based Activity Statistics (EAS); in Wales, the Patient Episode Database for Wales (PEDW) derived from the Admitted Patient Care dataset. Participants will be asked to consent to the sharing of their identifiable data (NHS number, date of birth, postcode and gender) and the trial ID with NHS Digital (or equivalent) in order to link to their record. NHS Digital (or equivalent) will then provide the University of Oxford with a pseudonymised dataset containing their personal data only identified with their trial ID number. The linkage file will be destroyed by the trusted third party once the linkage is complete.

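### Section 11.6 declares linked hospital use free of missing data, but the sources named for Scotland and Wales cover admitted care only, so a missing outpatient or emergency record there does not mean no use

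*Protocol*

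**What the plan says.** Section 11.6 makes the claim twice. For the validation of patient-reported hospital use it says that "missing data will not be a problem as a record of hospital attendance in HES will be the only marker required". Later, where it contrasts hospital use with OMAS and EQ-5D, it says that "hospital resource use observed in HES will not carry a risk of missing data". Multiple imputation is then planned for the two outcome measures, not for hospital use.

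The validation covers three kinds of attendance: "HES inpatient, outpatient and A&E attendances during the 12-month trial duration will be compared to what was reported by patients through CRFs". Its population is limited by consent only: "we will restrict the analysis to those trial participants who give consent to our accessing their hospital records". The 5-year cost-effectiveness model takes its hospital costs from HES as well.

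Section 7 places recruitment in "a minimum of 26 hospital orthopaedic departments within the UK". Section 9.3 lists the administrative sources by nation. For England these are the admitted, emergency, outpatient and critical care datasets within HES. For Scotland it is SMR01, whose title limits it to inpatient and day-case activity. For Wales it is "the Patient Episode Database for Wales (PEDW) derived from the Admitted Patient Care dataset". For Northern Ireland it is an acute, episode-based activity dataset (EAS), with no statement of which attendance types it contains.

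**The concern.** A record can serve as the sole marker of use only if the source would have captured the attendance had it occurred. For outpatient and emergency visits, the Scottish and Welsh sources as described do not meet that condition. A blank there means not observed. Section 11.6 does not draw the distinction, and it rules out missing-data handling for hospital use in advance.

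Two of the three long-term objectives in section 11.6 rest on these data. The validation compares two data sources on the same people, so balance between arms gives it no protection: patients who report correctly would look like over-reporters. In the 5-year model, the outpatient and emergency component of cost would be understated while admitted care was counted in full.

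**Working it through.** The protocol gives no figure to reproduce here, so the check sets the sections side by side and then shows how the effect scales.

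**Step 1. What each named source covers, by its description in section 9.3**

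| Nation | Admitted care | Outpatient | Emergency |
|---|---|---|---|
| England (HES) | yes | yes | yes |
| Scotland (SMR01) | yes (inpatient and day case) | not covered | not covered |
| Wales (PEDW) | yes | not covered | not covered |
| Northern Ireland (EAS) | not stated | not stated | not stated |

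**Step 2. The rule in section 11.6.** The rule is that "a record of hospital attendance in HES will be the only marker required to identify the use of resources". Applied to a source without outpatient or emergency data, it reads every such visit as no use.

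**Step 3. Two readings of the term HES in section 11.6.**
- HES as shorthand for all four national sources: outpatient and emergency use is unobserved for participants treated in Scotland or Wales.
- HES as the English database only: participants treated in Scotland or Wales have no linked hospital record of any kind.

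On either reading, the no-missing-data statement fails for those participants. No section excludes them.

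**Step 4. Scaling.** Let s be the share of linked participants whose source lacks outpatient and emergency data. Assume that true use is the same for them as for the rest, that patients report correctly, and that a blank is scored as zero.
- Recorded mean use = (1 − s) × true mean use.
- Apparent over-reporting = 1/(1 − s) − 1.
- A between-arm difference in this cost component is multiplied by (1 − s), if s is also alike in both arms. Centre is a minimisation factor (section 9.4), which makes that likely.

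| Assumed s | About how many of 890 | Recorded/true mean | Apparent over-reporting | A true £200 difference (hypothetical) becomes |
|---|---|---|---|---|
| 0% | 0 | 1.00 | 0% | £200 |
| 5% | 44 | 0.95 | 1/0.95 − 1 = 5.3% | £190 |
| 10% | 89 | 0.90 | 1/0.90 − 1 = 11.1% | £180 |
| 20% | 178 | 0.80 | 1/0.80 − 1 = 25.0% | £160 |

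The shares are assumptions, because the protocol gives neither sites nor participants by nation.

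**The case against.** The strongest reply is that the sentences speak of HES, that section 9.3 lists outpatient and emergency datasets within HES, and that for participants linked to HES nothing conflicts. This is fair for England, and it is why the statements need qualifying and not deleting. It does not rescue the text for participants treated in Scotland or Wales, who on that reading have no linked record at all, while the validation is limited by consent and not by nation.

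Other points stand in part:
- **Zero-counting is an inference.** A reader might infer that the protocol says zeros will be entered for these participants. It does not. The inference follows from the marker rule, the only rule given, if they enter the analyses.
- **Northern Ireland.** A reader might infer that no source outside England holds outpatient or emergency data. The protocol does not say what EAS contains, so the point is limited to Scotland and Wales.
- **Size.** UK-wide recruitment permits sites outside England but does not show that there are any. The share could be nil, and then there is no effect.
- **Other data.** The 12-month review of hospital records (section 9.10) and the participant questionnaires give first-year hospital use from other sources. That limits the harm to first-year costs. It does not help the validation, which needs the linked data as comparator, or later years.
- **Left to the analysis plan.** How national extracts are combined is ordinary analysis-plan detail. An explicit statement that no data can be missing is not: the protocol makes it, and its own list of sources contradicts it.

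**Conclusion.** The concern holds in a limited form. The no-missing-data statements in section 11.6 are wrong for outpatient and emergency attendances of any participant treated in Scotland or Wales, on the descriptions in section 9.3. For Northern Ireland the question is open.

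If the marker rule is applied to such participants, the artefact grows with their share: about 5%, 11% or 25% apparent over-reporting, and a 5%, 10% or 20% understatement of the outpatient and emergency cost component, for assumed shares of 5%, 10% or 20%. This rests on equal true use across nations and correct patient reporting. The real share is unknown.

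The point should not be read as touching the main trial result. The primary OMAS analysis at four months and the 12-month economic evaluation do not rest on linkage. Only the validation and the 5-year cost-effectiveness analysis, both reported separately, are affected. It is worth correcting before the linkage is carried out.

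**What to change.** In section 11.6:

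1. Qualify both statements so that they apply only where the participant's linked source holds the attendance type in question.
2. Restrict the outpatient and emergency part of the validation, and the outpatient and emergency cost inputs to the 5-year model, to participants whose linked source contains those attendances. As named, that is England; add Northern Ireland if its dataset is confirmed to hold them.
3. For all other participants, treat these fields as missing and not as zero. Any imputation should be a sensitivity analysis. The planned chained-equations model is for OMAS and EQ-5D; imputing use that is unobserved for a whole nation would be a new model, resting on an untestable assumption that use is alike across nations.
4. Keep admitted-care data for every nation whose source holds them.
5. State whether HES in section 11.6 means the English database or all the national sources in section 9.3.

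The cost is a few sentences, a smaller outpatient and emergency validation sample, and slightly wider cost intervals. With equal variance, the interval for that component widens by a factor of 1/√(1 − s): 1/√0.95 = 1.03, 1/√0.90 = 1.05 and 1/√0.80 = 1.12 for the three assumed shares. Carrying the restricted estimate over to all participants still assumes similar use across nations, which should be stated. If no participant was treated outside England, the change costs nothing.
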